10. MEASUREMENT OF EFFECT

10.1 Anti-tumor Effect

Subjects will be seen in follow-up at 1, 3, 6, 9, and 12 months following SRS.At each follow-up, neurologic history and examination will be done. MRI with gadolinium will be obtained at 3, 6, 9, and 12 months.

10.1.1 **Definitions**

Early radiation toxicity is defined as those observed within 30 days of SRS. Late radiation toxicity is defined as those observed after 30 days following SRS. Tumor response will be measured using MRI with gadolinium obtained at 3, 6, 9 and 12 months following SRS.

10.1.2 **Disease Parameters**

Target lesion is defined as those treated with radiosurgery. The size and volume of the target lesion will be measured using the treatment planning software.

10.1.3 Methods for Evaluation of Measurable Disease

MRI with gadolinium will be obtained at 3, 6, 9, and 12 months following SRS.

10.1.4 **Response Criteria**

10.1.4.1 Evaluation of Target Lesions

Radiographic response using MRI with gadolinium will be used. Follow-up MRI scans will be obtained at 3, 6, 9, and 12 months following SRS. Size of the treated lesion will be measured and compared to its pre-treatment size. Local tumor progression is defined as the radiographic appearance of a new or increasing enhancing lesion within the radiosurgical target volume. Local control is defined as lack of progression (P – below). Metabolic imaging may be necessary at times to distinguish tumor progression from treatment related radiation necrosis.

- 4.1.3.4.1. Complete response (CR): The tumor is no longer seen on the follow-up MRI scan.
- 4.1.3.4.2. Partial response (PR): Decrease of >50% in the product of two diameters on the follow-up MRI scan.

- 4.1.3.4.3. Minor response (MR): Decrease of <50% in the product of two diameters on the follow-up MRI scan.
- 4.1.3.4.4. Stable disease (SD): The scan shows no change.
- 4.1.3.4.5. Progression (P): A >25% increase in tumor area (product of two diameters).

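### Section 10.1.4.1 gives two unreconciled definitions of local progression, and the one tied to local control names only pre-treatment size as comparator, so regrowth after a response can be scored as controlled

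*Combined protocol and SAP*

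**What the plan says.** All the relevant wording is in section 10.1.4.1 of the protocol.

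- Comparator for size: "Size of the treated lesion will be measured and compared to its pre-treatment size". No other reference scan is named.
- Narrative definition: "Local tumor progression is defined as the radiographic appearance of a new or increasing enhancing lesion within the radiosurgical target volume". It carries no size threshold and no reference scan.
- Local control: "Local control is defined as lack of progression (P – below"). The parenthesis points to the response list.
- Category P in that list: "A >25% increase in tumor area (product of two diameters"). This entry names no reference scan of its own.
- Partial response (PR): "Decrease of >50% in the product of two diameters on the follow-up MRI scan". Complete response (CR): "The tumor is no longer seen on the follow-up MRI scan".
- Schedule: "Follow-up MRI scans will be obtained at 3, 6, 9, and 12 months following SRS".

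Section 10.1.6 times progression from SRS. Section 10.1.7 (Response Review) is marked not applicable. Local control is a secondary objective (1.2.1) and the first secondary endpoint (12.1.2.1).

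**The concern.** The two definitions can give different answers for the same scan. Take a lesion that shrinks after SRS and then grows on successive scans. If the narrative sentence governs and growth is judged from the preceding scan, this is progression as soon as growth is seen. If P governs and is judged against pre-treatment size, the lesion stays controlled while it regains all the ground it lost and a further 25% of area.

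The local control sentence points to P, so the more lenient rule is the likelier one to be applied. Failures that take the form of regrowth after a response would then be missed or dated late. Local control and time to progression would look better than they are. Improved local control is part of the hypothesis in the synopsis, and sections 2.4 and 2.5 cite local control rates beside which the result will naturally be read.

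**Working it through.** The plan gives no target rate, power or event count for local control, so there is no stated figure to reproduce. The check is threshold arithmetic.

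**Inputs.** The 25% threshold for P and the pre-treatment comparator come from 10.1.4.1. The shrinkage *s*, as a fraction of the pre-treatment product of diameters, is an illustrative assumption from 25% to 90%; the documents give no response depths.

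**Formulas**, with the pre-treatment product set to 1:

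- Nadir = 1 − s.
- P against pre-treatment size needs a product above 1.25, which is 1.25/(1 − s) times nadir.
- P against nadir needs a product above 1.25 × (1 − s).

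| Shrinkage s | Nadir | Multiple of nadir needed, pre-treatment reference | P reached at, nadir reference (% of pre-treatment area) |
|---|---|---|---|
| 25% | 0.75 | 1.25/0.75 = 1.67 | 93.8% |
| 50% | 0.50 | 1.25/0.50 = 2.5 | 62.5% |
| 75% | 0.25 | 1.25/0.25 = 5 | 31.2% |
| 90% | 0.10 | 1.25/0.10 = 12.5 | 12.5% |

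With a nadir reference the required multiple is 1.25 in every row. With the pre-treatment reference P is reached only above 125% of pre-treatment area in every row.

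**Example.** A 3 × 3 cm lesion has a product of 9 cm². It halves to 4.5 cm². Against nadir, P is reached above 1.25 × 4.5 = 5.6 cm². Against pre-treatment size, it is reached above 1.25 × 9 = 11.25 cm², a diameter of 3.0 × √1.25 = 3.35 cm if round. Between those two values the lesion is controlled under one reference and failed under the other.

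**Gap in the list.** Stable disease is described as an unchanged scan. A lesion up to 25% above its pre-treatment area therefore fits no listed category. It is still not P, so it counts as controlled.

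**Which lesions.** Both arms are post-resection (4.1.3.1, 12.2). The shrink-and-regrow pattern needs a measurable lesion at the start: residual enhancement after surgery, or an unresected lesion. Section 4.1.2 sends patients who are not surgical candidates to primary SRS, and 4.1.3.3 allows an unresectable lesion as target. For a cavity with no measurable residual there is no lesion area on which to base a percentage, and only the narrative sentence clearly covers failure there.

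**The case against.** The strongest reply is that the narrative sentence already deals with regrowth. Taken literally, a responder whose enhancement grows on the next scan is progressing, and reappearance after CR is new enhancement; both would count below the original size. The P entry names no reference scan, so applying pre-treatment size to it is an inference. Both defined arms are also post-resection, where failure will often appear as new enhancement in the cavity.

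Much of this stands. It rules out the flat claim, which a reader might infer, that the plan ignores regrowth until the lesion exceeds its original size. The narrative sentence contradicts that, and under P the cut-off is 125% of original area, not 100%. The post-resection arms also narrow the set of lesions affected.

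The reply does not remove the problem. The local control sentence refers to P, the only comparator named is pre-treatment size, and no review step is described that would settle a disagreement. Two readers following the text could score the same scan differently.

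Two further inferences are not supported. One is that failure will be dated a visit or more late, or after month 12: no regrowth frequency or growth rate is given. The other is that deeper responses at higher doses would exaggerate a dose effect. That is conditional on such responses, no comparison of local control between dose levels is specified, and 12.2 rules out subset analysis.

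**Conclusion.** The point holds as a definitional conflict with a likely direction of bias. Section 10.1.4.1 does not say which definition of local progression governs or against which scan P is judged. On the reading that its cross-reference favours, a measurable lesion that responds and regrows is controlled until it passes 125% of pre-treatment area, or 2.5 times nadir after 50% shrinkage and 5 times after 75%.

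Those multiples are exact for the assumed shrinkages. They describe the scoring threshold and not the error in the local control rate. That error depends on how many lesions are measurable, respond and then regrow, and the documents give none of these. The maximum tolerated dose, the dose-limiting toxicity rules and the maximum of 60 subjects are unaffected. This is an inexpensive improvement to a secondary endpoint that should be made before local control is analysed.

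**What to change.** In 10.1.4.1:

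1. Keep the pre-treatment scan as the reference for complete, partial and minor response.
2. State one governing definition of local progression, used for both local control and time to progression. It is met by either of the following: an increase of more than 25% in the product of two diameters over the smallest value recorded since and including the pre-treatment scan; or new or reappearing enhancement within the target volume, including in a cavity with no measurable residual and after CR.
3. Set a minimum absolute increase before analysis, so that measurement error around a very small nadir is not scored as failure.
4. Reword the narrative sentence to match, so that only one definition remains.
5. State that the metabolic imaging already mentioned in 10.1.4.1, where it has been obtained, is taken into account before local failure is scored.

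The cost is a few sentences, with no added scheduled MRI or patients, because the lesion is already to be measured on each follow-up MRI. The reported local control rate may be somewhat lower. A lower threshold will also bring more enhancement due to radiation necrosis into question, which is the reason for item 5.

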4.2 General Concomitant Medication and Supportive Care Guidelines

Supportive treatment may include anti-emetics, anti-diarrheal medications, antipyretics, anti-histamines, analgesics, antibiotics, and others, such as blood products. Patients will be permitted to receive appropriate supportive care measures as deemed necessary by the treating physician.

Steroids may be given after each SRS treatment to decrease the risk of CNS symptoms due to cerebral edema. In addition, steroids may be used as required to control CNS symptoms due to tumor-associated or RT-associated cerebral edema, but wherever possible, should be tapered and stopped.

Nausea/vomiting: Nausea and vomiting should be treated aggressively. In particular, the use of antiemetics including 5HT3 antagonists and/or dexamethasone is encouraged. Patients should be strongly encouraged to maintain liberal oral fluid intake during therapy.

4.3 **Duration of Therapy**

SRS will be given in 3 fractions, each approximately 24 hours apart.

4.4 **Duration of Follow Up**

Follow-up schedule is summarized in section 9. Study Calendar.

Patients will be seen in follow-up at 1st, 3rd, 6th, 9th, and 12th months following radiation. The following will be obtained at pre-treatment evaluation and at each follow-up time point: Neurologic history and physical examination, KPS, steroid use assessment, and toxicity evaluation. MRI with gadolinium will be obtained at pre-treatment and at 3, 6, 9, and 12 months following treatment until progression is documented and continuing every 3 months for those without evidence of intracranial progression.

After the first 12 months, patients will be followed every 3-6 months at the discretion of the patient's physician. At each visit, interval history, physical exam, KPS, toxicity evaluation, and brain MRI scans will be obtained.

For those subjects who are unable to come for clinic visits, clinical follow-up information will be obtained via 1) a phone call to the patient and/or 2) clinic source document from his/her local physician. For subjects unable to appear in person for clinic visits, HRQOL questionnaires will be completed via a telephone interview or mail.

For patients unable to return for imaging studies, source documents from outside institutions will be used to document imaging follow-up.

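### The local control rule cannot score a new nodule in an empty resection cavity, the baseline scan is not named, and a separate new lesion 0–5 mm outside the target is neither local nor distant failure

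*Combined protocol and SAP*

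**What the plan says.** Section 10.1.4.1 first gives a rule with no size threshold: "Local tumor progression is defined as the radiographic appearance of a new or increasing enhancing lesion within the radiosurgical target volume". The local control endpoint is then tied to a response category: "Local control is defined as lack of progression (P – below". That category reads "Progression (P): A >25% increase in tumor area (product of two diameters". The neighbouring categories include "Partial response (PR): Decrease of >50% in the product of two diameters on the follow-up MRI scan" and "Stable disease (SD): The scan shows no change".

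On the comparator, 10.1.4.1 says "Size of the treated lesion will be measured and compared to its pre-treatment size". Section 4.4 says "MRI with gadolinium will be obtained at pre-treatment", and the Study Calendar (section 9) shows one Pre-Entry MRI. Section 10.1.2 adds "Target lesion is defined as those treated with radiosurgery" and has its size measured in the treatment planning software.

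Section 10.1.4.2 counts a lesion as distant brain failure only if it lies farther than 5 mm from the target volume.

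The primary objective (1.1) concerns resection cavities, and both arms in 4.1.3.1 and 12.2 are post-resection. Sections 4.1.2 and 4.1.3.3 still provide for lesions that are not resected. For a cavity, the target is the cavity plus 2 mm (4.1.3.3). Local and distant brain control are secondary endpoints (12.1.2). Section 10.1.6 starts time to progression at SRS without saying which progression rule applies.

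**The concern.** After resection the typical local failure is new enhancement in a cavity that held no measurable tumour. A percentage change from baseline does not describe that event. If the endpoint follows P literally, the event cannot be scored. If it follows the preceding sentence, it is a failure. Two readers of the same MRI could therefore code the same patient differently, and 10.1.7 (Response Review) is marked not applicable, so no review step is described to settle it.

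The unnamed baseline adds to this, because the 25% threshold means something different before and after resection. The gap between the local and distant definitions means that a recurrence just beyond the treated margin can drop out of both failure counts.

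The synopsis hypothesises better local control than with single-fraction SRS, and sections 2.4 and 2.5 cite published control rates (88% and 79% for cavities at 6 and 12 months; 49% and 45% for lesions of 2–3 and 3–4 cm). Setting the trial's result beside such figures requires one definition of failure.

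**Working it through.** The plan gives no figure for this point to reproduce. The check is a comparison of definitions, with arithmetic to show the size of each gap.

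**1. The two rules side by side**

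| Finding on MRI | First sentence of the definition | Lack of P |
|---|---|---|
| New nodule in target, no residual at baseline | progression | undefined |
| Measurable residual, growth above 0 and up to 25% | progression (increasing) | control |
| Measurable residual, growth above 25% | progression | progression |

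- Row 1: percentage change = (A_follow-up − A_baseline) / A_baseline. With A_baseline = 0 there is no value.
- Row 2, example: growth from 1.0 × 1.0 cm to 1.1 × 1.1 cm gives 1.21/1.00 − 1 = +21%. This is increasing, is not P, and is not stable disease, which requires no change.
- P requires each diameter to grow by √1.25 − 1 = 11.8%, that is 2.4, 3.5 and 4.7 mm for lesions of 2, 3 and 4 cm.

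**2. The baseline**

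- Pointing to pre-SRS: the target lesion is what receives radiosurgery and is measured in planning software (10.1.2). The follow-up MRIs that 4.4 dates from treatment are dated from SRS in 10.1.
- Pointing to pre-surgery: 4.1.1 is headed as pretreatment evaluation and includes the assessment for surgery.
- Neither 4.4 nor the Study Calendar places the scan before or after resection.

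Illustration of the less-supported, pre-operative reading, for a new 2 × 2 cm nodule (4 cm²):

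| Pre-operative tumour | Area | Change | P reached above |
|---|---|---|---|
| 2 × 2 cm | 4 cm² | 4/4 − 1 = 0% | 1.25 × 4 = 5 cm² |
| 3 × 3 cm | 9 cm² | 4/9 − 1 = −56% | 1.25 × 9 = 11.25 cm² |
| 4 × 4 cm | 16 cm² | 4/16 − 1 = −75% | 1.25 × 16 = 20 cm² |

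On size alone, the first would be stable disease and the other two partial responses. On the better-supported pre-SRS reading with no residual, the result is row 1 of the first table: undefined.

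**3. The unassigned zone**

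Local means inside the target; distant means farther than 5 mm from it. A separate new lesion 0–5 mm outside, including exactly 5 mm, is neither. P carries no location limit, so growth of a treated lesion across the target edge may still count.

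To show the extent of the zone, use V = (4/3)πr³. Spheres of 2, 3 and 4 cm diameter give 4.19, 14.14 and 33.51 cm³, matching the protocol's 4.2, 14.1 and 33.5 cm³. Assume the cavity equals that sphere; the target then has radius r + 0.2 cm and the zone extends to r + 0.7 cm.

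| Diameter | Target (cavity + 2 mm) | 0–5 mm zone | Zone / target |
|---|---|---|---|
| 2 cm | 7.24 cm³ | 13.34 cm³ | 1.84 |
| 3 cm | 20.58 cm³ | 24.02 cm³ | 1.17 |
| 4 cm | 44.60 cm³ | 37.85 cm³ | 0.85 |

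These are volumes, not recurrence frequencies.

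**4. Scale**

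The maximum per arm is 30 evaluable subjects (12.3.1), so one reclassified patient moves a crude rate by 1/30 = 3.3 points. The documents do not say whether the rates are crude or actuarial.

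**The case against.** The strongest reply is that the two sentences can be read together. The local control sentence directly follows the definition of local progression. On that reading, new enhancement covers a cavity without measurable tumour, and P supplies the threshold for an increase in a measurable lesion. The response scale suits the unresected lesions that 4.1.2 and 4.1.3.3 still mention. This is a sensible reading, so a claim that the rules are irreconcilable would go too far. What stands is that the protocol does not state it. The sentence defining the endpoint points to P alone, and P fails for the population both arms describe.

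A reader might also infer that a 2 cm cavity nodule would be reported as a partial response. That needs a pre-operative baseline, which 10.1.2 and the follow-up wording tell against, and it needs the reader to ignore the first definition. The figures illustrate why the baseline should be named; they do not predict what the trial will report.

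A third inference is that every recurrence within 5 mm of the target is lost. Contiguous growth may still be P, so only separate new lesions are unassigned.

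Finally, 3.3 points per patient holds for any binary endpoint in an arm of 30. It gives scale and is no measure of how often the problem arises.

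**Conclusion.** The point holds in this form. Section 10.1.4.1 does not say how the two local-failure rules fit together, and the one attached to local control cannot score new enhancement in a cavity with no residual tumour. The baseline scan is not fixed. Sections 10.1.4.1 and 10.1.4.2 together leave a separate new lesion 0–5 mm outside the target uncounted. Taken literally, these rules can miscount failures on two listed secondary endpoints and leave time to progression unclear, so the wording should be corrected.

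A reader might infer that the MTD is in doubt. It is not: DLT and escalation rest on CNS toxicity grades and do not use these definitions. Nor does the missing label for growth up to 25% by itself change local control, which is binary if P governs.

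The number of affected patients cannot be derived from the documents. The zone volumes assume a spherical cavity equal to the original tumour, and the 3.3 points assume a crude rate in a full arm of 30.

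**What to change.** In 10.1.4.1, state that:

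- a new enhancing lesion within the target is local failure whatever the percentage;
- for tumour measurable at baseline, an increase counts as progression only when it meets P (above 25%);
- the baseline is the post-operative, pre-SRS imaging used to define the target, or the pre-SRS imaging for an unresected lesion;
- the existing provision for metabolic imaging to separate progression from necrosis is kept.

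In 10.1.4.2, assign separate lesions 0–5 mm outside the target, including exactly 5 mm, to one stated category and tabulate them separately, so that each recurrence counts once. In 10.1.6, use the same definitions for time to progression.

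The cost is mainly wording. If the Pre-Entry MRI turns out to precede surgery, the Study Calendar must also name the post-operative, pre-SRS imaging. Contouring the cavity already requires some post-operative planning imaging, though not necessarily a gadolinium MRI. The downsides are that the reported control rate may be slightly lower, some treatment-related enhancement may be scored as failure, and placing the 0–5 mm zone is a convention, which is why it should be shown separately.

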8. CORRELATIVE/SPECIAL STUDIES

- 8.1.Dose heterogeneity and conformality within the target volume will be calculated for each lesion to investigate whether these factors have any correlation to local control or toxicity.
- 8.2.To identify potential predictors of response, the following pre-treatment tumor characteristics will be collected:
 - 8.2.1. Lesion size
 - 8.2.2. Histology
 - 8.2.3. Pattern of enhancement on MRI scan
 - 8.2.4. Presence or absence of extensive edema

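### The tumour-response categories in Section 10.1.4.1 leave increases of up to 25% uncoded and put no tolerance around stable disease

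*Combined protocol and SAP*

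**What the plan says.** Section 10.1.4.1 compares each treated lesion's size at 3, 6, 9 and 12 months with its size before treatment. It gives five outcomes:

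- "Complete response (CR): The tumor is no longer seen on the follow-up MRI scan"
- "Partial response (PR): Decrease of >50% in the product of two diameters on the follow-up MRI scan"
- "Minor response (MR): Decrease of <50% in the product of two diameters on the follow-up"
- "Stable disease (SD): The scan shows no change"
- "Progression (P): A >25% increase in tumor area (product of two diameters"

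Section 10.1.2 says size is measured in the treatment planning software. No section gives a tolerance for no change, a rounding rule or a default category. Response review (10.1.7) is marked N/A.

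The narrative in Section 10.1.4.1 counts any new or growing enhancement inside the target volume as local progression, with no size threshold. It then defines local control as the absence of category P.

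Response also appears in Section 8.2: "To identify potential predictors of response, the following pre-treatment tumor characteristics will be collected".

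**The concern.** A response scale should give every scan exactly one code, and stable disease should absorb changes too small to distinguish from reading error. This scale does neither. Stable disease is a single point rather than a band. Every measured decrease below 50%, however small, moves a lesion to MR, and every measured increase up to 25% leaves it with no code.

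At stake is whether a table of response categories can be filled in and read. Staff meeting a 10% increase have no rule to follow. A reader meeting a row of minor responses cannot tell real shrinkage from re-measurement. If the Section 8.2 work takes these categories as its outcome, lesions with little real change would be sorted largely by the sign of the reading error.

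**Working it through.** The plan states no expected response rate or distribution, so there is no figure to reproduce. The check is one of logic first, then of size.

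**1. Coverage.** Apply the five definitions to a percentage change in the product of two diameters:

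| Change | Category |
|---|---|
| −60% | PR |
| exactly −50% | none |
| −49%, −1% | MR |
| 0% | SD |
| +0.1%, +10%, +25% | none |
| +25.1% | P |

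This needs no assumptions. For scale, take a 20 × 20 mm lesion. One millimetre more in both diameters gives 441/400 − 1 = +10.25%, which is uncoded. One millimetre less gives 361/400 − 1 = −9.75%, which is MR.

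**2. Share of unchanged lesions read as MR.** Suppose the lesion has not changed and the two scans carry independent errors from the same distribution. The log ratio of follow-up to baseline product is then symmetric about zero. With continuous measurement the follow-up product is smaller with probability 1/2, whatever the size of the error. Almost none of that half reaches a 50% decrease, so nearly all of it is MR.

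**3. Split of the other half.** This depends on an error size that the documents do not give. Assume lognormal error with a coefficient of variation (CV) of 3% to 10% per diameter, independent across two diameters and two scans. Let s = √ln(1 + CV²). The log ratio of products has mean 0 and SD 2s. Then:

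- MR = 0.5 − Φ(ln 0.5 / 2s)
- uncoded = Φ(ln 1.25 / 2s) − 0.5
- P = 1 − Φ(ln 1.25 / 2s)

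At CV 5%, 2s = 0.0999 and ln 1.25 = 0.2231. So 0.2231/0.0999 = 2.233 and Φ = 0.9872. Uncoded is 0.4872 and P is 0.0128.

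| CV per diameter | 2s | MR | Uncoded | P |
|---|---|---|---|---|
| 3% | 0.0600 | 50.0% | 50.0% | 0.01% |
| 5% | 0.0999 | 50.0% | 48.7% | 1.3% |
| 7% | 0.1398 | 50.0% | 44.5% | 5.5% |
| 10% | 0.1995 | 50.0% | 36.8% | 13.2% |

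False PR is at most 0.03%. Exact no change has probability essentially zero.

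**4. Rounding to whole millimetres.** A simulation with rounded diameters of 20, 30 and 40 mm and CVs of 3%, 5% and 10% gives exact no change in 1% (40 mm, 10%) to 24% (20 mm, 3%) of readings. MR takes 38% to 49% and the uncoded range 35% to 47%. Rounding helps but does not restore a usable stable category.

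**5. Four follow-up scans.** For an unchanged lesion the baseline reading and four follow-up readings are exchangeable. At least one follow-up reads below baseline unless the baseline is the smallest of the five, so the probability is 1 − 1/5 = 80%. Simulation gave 0.799.

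**6. What depends on these codes.** Section 12.1.2 lists local control, distant brain control, survival, adverse effects and quality of life as secondary endpoints; no response rate is among them. Best overall response (10.1.4.3) and duration of response (10.1.5) are N/A. Local control, as the absence of P, uses only the +25% boundary. The dose-finding endpoint uses toxicity alone.

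**The case against.** Four points have weight.

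*No change may be a visual judgement.* It is the only size-change category not written as a percentage of the diameter product. A radiologist who calls small differences unchanged would largely remove both the 50% and the uncoded share. This stands as a limit: the sizes above need the numeric reading. But the plan does not adopt the visual reading, the neighbouring categories are numeric, and Section 10.1.2 specifies measurement in software.

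*The error size is not in the documents.* True, so a range is shown. It affects the split between uncoded and P. The half read as MR does not depend on it, and neither does the coverage gap.

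*The arms are post-resection.* Sections 4.1.3.1 and 12.2 describe both arms as treated after resection, so a measurable 20 mm lesion is not the typical target. Sections 4.1.2 and 4.1.3.3 still provide for unresected lesions. The percentages therefore apply to measurable lesions only, not to every patient.

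*Little rests on the categories.* A reader might infer that the gap corrupts local control or the maximum tolerated dose. Step 6 of the working shows it does not. A reader might also infer that Section 8.2 uses these five categories as its outcome and would mostly model noise. Section 8.2 says only that characteristics will be collected to look for predictors of response. It names no outcome coding, does not pool MR with PR and specifies no model. Nor does the plan define a responder: the mislabelling is into minor response.

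**Conclusion.** The defect holds on the text: the scale is not exhaustive, MR has no floor and stable disease has no width. Its size, with no change read numerically, is about half of truly unchanged measurable lesions read as MR at any one scan. At an assumed 3% to 10% error per diameter, a further 50% to 37% have no code and 0.01% to 13% are read as P.

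The reach is limited to the descriptive tumour-response classification and, conditionally, the exploratory work in Section 8.2.

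There is one neighbouring risk. The only other text that could place a 0–25% increase is the narrative sentence on local progression, which conflicts with the definition of local control as lack of P. If staff used it to code such lesions, the inconsistency could reach the local control rate. That would come from the conflict between the two sentences, not from the stable/minor boundary, but the two are best settled together.

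**What to change.** Reword Section 10.1.4.1 so that the categories are exhaustive and do not overlap:

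- PR: a decrease of at least 50%, short of complete response.
- P: an increase of more than 25%.
- SD: everything between.
- MR: drop it, or keep it with a stated minimum decrease above measurement error.

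State that an increase of up to 25% is SD, and reconcile this with the sentence that counts any new or growing enhancement as local progression. If Section 8.2 is to use these categories, say which of them count as response.

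Under the assumptions above and with MR dropped, an unchanged lesion is coded SD with probability Φ(ln 1.25 / 2s) − Φ(ln 0.5 / 2s). That is 99.99%, 98.7%, 94.5% and 86.8% at CVs of 3%, 5%, 7% and 10%, against essentially zero now with continuous measurement. As an illustration only, keeping MR as a decrease of 25% to 50% gives SD in 99.99%, 98.5%, 92.5% and 79.4%, and false MR in about 0.0%, 0.2%, 2.0% and 7.4%. The false-P share does not change, because the +25% boundary stays.

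The cost is definition wording, with no added patients, visits or scans. The downside is that fewer lesions are labelled minor response.
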